2.7.2 Exclusion criteria

1. A Charlson Comorbidity Index score 5 or higher
2. Foot or leg size incompatible with available Magnes shoes or Aircast boot
3. Comorbidities:
 - a. concurrent or pre-existing injuries that impair the ability to use the orthosis as intended (e.g. neurological conditions including Multiple Sclerosis, brain injury, spinal cord injury);
 - b. patients with any other disorders involving restriction of mobility, limited ambulation on forearm crutches, or conditions affecting the fracture healing process (e.g. joint disease, neurological disorder, amputation)
 - c. BMI >35kg/m²
4. Require non-standard postoperative care
5. Not able to attend follow-up visits at the RBWH.
6. Have suffered any of the following fracture types:
 - a. talus fractures
 - b. pilon (tibial plafond) fractures
 - c. calcaneal fractures
 - d. stress fractures
 - e. ankle fractures associated with ipsilateral (mid)foot fractures
 - f. bilateral lower limb fractures
 - g. concomitant upper limb fractures or injury
 - h. Posterior malleolus fractures requiring posterior plating
 - i. small and undisplaced fractures that can be managed non-operatively
 - j. trimalleolar fractures with significant posterior involvement that are not suitable for early weight-bearing
 - k. open (compound) fractures or fractures on both lower limbs.

2.8 Study Intervention

Current practice in the orthopaedic clinics of the RWBH includes fitting all patients operated for an ankle fracture with an Aircast AirSelect Standard walker boot (**Figure 1A**) in the operating theatre. As such, patients will be screened and consented in the pre-operative phase.

The Aircast Airselect Standard walking boot (hereafter referred to as the Aircast boot or Aircast) is shown in Fig. 1A. The Aircast is considered part of standard care for these ankle fracture patients. In clinical practice, the Aircast boot is utilised for fractures of the foot, ankle and distal tibia or fibula, high-grade ankle sprains and for postoperative immobilisation. It offers several advantages over traditional casts such as allowing easier access to the surgical wound, the ability to adjust the Aircast boot depending on swelling and improved durability when used as a walking device.

Those patients who consent to participate in the study will be fitted with the Aircast boot as per usual practice with the addition of a Magnes device attached to the boot, as shown in **Figure 1A**, in the operating theatre following surgical fixation.

[figure not shown]

Figure 1: *The Aircast boot with the Magnes smart device (1A) and the Magnes NUSHU (1B) It has anterior and posterior semi-rigid outer shells that when tightened, using the three straps, immobilises and supports the ankle and provides protection. An inner lining protects the limb from skin irritation. The Aircast has two adjustable distal air cells within the shell that inflate to support the malleoli and provide compression to decrease swelling. The Aircast is available in sizes XS – XL, allowing a suitable fit for most patients.*

In addition, patients will receive a standard information and education leaflet designed for the study (Appendix 1). The information and education leaflet includes information about the smart devices and their care (smart device in the Aircast and the NUSHU shoe) and information on postoperative care (practical guide, weight-bearing, other activities and exercises). This leaflet will facilitate standardisation of the postoperative rehabilitation across patients. (Appendix 1).

Post-operatively patients will be offered up to 6 physiotherapy sessions in fortnightly intervals as per usual practice. (Appendix 2).

As the patients' rehabilitation progresses and restriction of movement is no longer necessary, patients will transition from the Aircast boot to the Magnes NUSHU. Typically, this will occur at

approximately 6 weeks post-operatively (**Figure 1B**). Patients will be asked to wear the NUSHU when they are no longer wearing the Aircast boot, for walking and other activities.

The Magnes NUSHU contains the same technology as the Aircast (it is fitted with a weight-bearing sensor, and records weight-bearing and activity data in the same way). Patients will be asked to wear the Magnes NUSHU shoes until the end of the study (12 weeks postoperatively).

2.9 Immediate postoperative care

As mentioned above, the Aircast boot will be applied in theatre, over the surgical dressings, without inflation, and is to be left on until the first Orthopaedic follow-up appointment at approximately 2 weeks. However, the Aircast boot is designed to make it easy to don and doff, so that circulation and wound healing can be assessed during routine postoperative care.

A physiotherapist will review each patient postoperatively, before the patient leaves hospital and give instructions about how the use of the Aircast boot, the maintenance of the Magnes device (charging, positioning etc), crutches and demonstrate, instruct and educate the patient with regard to the rehabilitation plan.

2.10 Use of Smart device during postoperative rehabilitation

The Aircast boot will be fitted with the Magnes smart device, removing the need for the patient to interact with the device for any other reason than to charge its battery. As mentioned above the Magnes smart device has a battery life of appx 16 hours. Patients will be advised to charge the battery every day and will be instructed on how to do this, before they leave the hospital.

The Magnes device has the capacity to automatically synchronise data when it is connected to the designated Hospital based WiFi network. Data will be downloaded from the Magnes device during each follow-up appointment (**Error! Reference source not found.**) and each physiotherapy appointment visit, every 2 weeks. The NUSHU shoe works in the same way as the Magnes smart device, and the same regime (regarding data download) will be followed.

3.0 Outcome measures

As this is a feasibility study the key outcomes to focus on are feasibility outcomes. As such the study will focus on the feasibility of the use of the Magnes device by the patient and the clinician.

3.1 Magnes Device specific Outcome Measures

The Magnes Device uses a lithium polymer battery and can collect approximately 16 hours of data on a single charge and can store data equivalent to 25 days of use. It can record gait parameters (i.e. step velocity, step length, swing time, step time, stance time) and the loading behaviour (i.e. peak load, average load, load duration, steps/day). Force is recorded in Newtons (N). The boot communicates to an iPhone/iPad application via Bluetooth low energy to start/stop data collection. The data are transferred to the smartphone/iPad via WLAN.

Aim 1:

The patient acceptability and feasibility of using this device in the Aircast boot during rehabilitation (week 1 to approximately week 6)

Feasibility

- Percentage of weight-bearing per week
- The correlation between instructed amount of weight-bearing and actual weight-bearing, in both intensity and total time.

Acceptability

- Ability to maintain charge in device
- Adverse events recorded relevant to the use of the Magnes smart device
- Open-ended /a semi-structured phone interview after Assessment 3 (12 weeks postoperatively) will be conducted and analysed to gain insight in the acceptability of using the Magnes smart device in the Aircast boot during postoperative rehabilitation. Every second participant will be selected to receive a phone call (participants 2, 4, 6, 8, 10, 12).

Aim 2:

The patient acceptability and feasibility of using the Magnes NUSHU during rehabilitation (from approximately week 6 to week 12)

Feasibility

- Time to fully weight-bear
- Percentage of weight-bearing per week
- The correlation between instructed amount of weight-bearing and actual weight-bearing

Acceptability

- Ability to maintain charge in device
- Adverse events recorded in regard to the Magnes smart device
- Semi-structured phone interview after Assessment 3 (12 weeks postoperatively) will be conducted and analysed to gain insight in the acceptability of using the Magnes smart device in NUSHU during postoperative rehabilitation.

Aim 3:

The clinician acceptability and usability of the data recorded by both devices (Magnes and NUSHU), for clinical decision-making

Feasibility

- Ability to upload data consistently during the exhibition phase

Acceptability

- A semi-structured interview will be conducted and analysed to gain insight in the usefulness of using data collected with the smart devices to inform clinical decision making.

The **clinical outcomes** of ankle rehabilitation will be evaluated using the AFORM questionnaire (8). This is a validated outcome measure for patients with ankle impairment and has been shown to possess high validity and reliability. It is a patient reported outcome measure, which is condition specific for use in clinical and research settings among patients who suffered an ankle fracture. The A-Form is comprising of 8 questions assessing activities of daily life and sporting activities. (Appendix 4)

Additional measurements will include health related quality of life measured using the EQ-5D 5L (EuroQol five-dimension health utility tool) which will be taken at all 3 points (at 2, 6 and 12 weeks post-operatively). The EQ-5D 5L is used to measure health utility and can be used to value health services in terms of quality-of-life improvement. It is not disease-specific and therefore enables

comparison across different diseases. Health utility measures are important for cost-effectiveness analysis and data from the EQ-5D 5L will enable economic evaluation of changes to health services as a result of introducing this new technology.

Data from the Magnes device will be downloaded at each fortnightly physiotherapy appointments (Appendix 2). The Magnes device provides data in force measurements (Newtons) which will be interpreted as weight-bearing and will be plotted to show the gradual increase through the period of rehabilitation and recovery.

Baseline measurement will be taken at the first postoperative appointment at 2 weeks post-surgery. Subsequent measurements will be taken at 6 and 12 weeks. If patients miss their follow-up appointments, the research nurse will call the patient and collect the outcome measures over the phone. Sensor data will be collected on the next visit of the patient to the clinic.

Objective measurements of ankle dorsiflexion, plantar flexion, eversion and inversion will be taken by the research physiotherapist using a goniometer as per standard clinical practice.

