4.0 Data collection

Data will be collected at 2 weeks post-surgery (baseline for this study), and at 6- and 12-weeks follow-up. Non identifiable baseline data, such as gender and age, will be recorded, in addition to non-identifiable health related data, for example, date of injury, injury cause, imaging reports and type of surgery. This information will be recorded on a secure, password protected Metro North REDCap server. See Appendix 5 for a pdf of the REDCap data dictionary. Range of movement, AFORM and EQ-5D 5L: measures will be taken at each follow-up visit.

Table 1: Outcomes to be recorded at patient follow-up visits

No.	Measurement	Description	When measured
Ability to use technology: insoles and iPad App			
1.	Data upload	Has the data been uploaded to the cloud successfully for the time period in question	2, 6, 8, 10 and 12 weeks
2.	Device charging and monitoring	How long each day did the patient wear the boot/shoe? Did the device remain charged (and able to record data) for the time period in question? Were there any problems related to keeping the battery charged?	2 weeks, 6 weeks, 12 weeks
3.	Other issues raised by the patient	Description of any other problems faced by the patient that limit their ability to use the device and capture data.	2 weeks, 6 weeks, 12 weeks
4.	Ownership of a smartphone	Patients will be asked if they own a smartphone (necessary as the future randomised trial will require this)	At recruitment
Patient Reported Outcome Measures			
5.	AFORM	Standardised questionnaire, filled in by the patient.	2, 6 and 12 weeks
6.	EQ-5D 5L: EuroQol five-dimension health utility tool	Standardised questionnaire, filled in by the patient.	2, 6 and 12 weeks
7.	Return to work	Has the patient returned to work? Is the patient able to return to work?	2, 6 and 12 weeks
8.	Medication review	Consumption of OTC and prescription analgesics	Daily for 12 weeks
Other clinical measures			
9.	X-ray ankle	XR ankle: WB out of cast – AP/lateral/mortise	6 weeks
10.	Wound review	Orthopaedic Department Nurse	2 weeks
11.	Weight-bearing	Magnes Sensor Data	2-6 -8*-12 weeks

No.	Measurement	Description	When measured
12.	Complications	Orthopaedic Department Nurse	Throughout the duration of the project
Range of Motion Measures			
13.	Ankle dorsiflexion (DF)	Measured using a standard goniometer	2, 6 and 12 weeks
14.	Ankle dorsiflexion (DF) (knee to wall)	Measured using a standard ruler	2, 6 and 12 weeks

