6.0 Risks and Benefits

This study is not changing any aspect of standard clinical practice in the treatment and rehabilitation of ankle fractures so there is no additional risk from participating. The only additional burden is that the participant will complete two questionnaires at three timepoints and they will be required to charge the Magnes device once a day. There will be no direct benefit to individuals as a result of participating in this study. However, they will indirectly contribute to advances in ankle fracture rehabilitation practices, and in streamlining aftercare in this population. Participants will not be reimbursed for their time.

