APPENDIX 1: Rehabilitation protocol

Ankle Fracture - Post operative Physiotherapy

The following is a guide only, please check for any changes or variances as indicated by your surgeon's post-operative plan.

(Excludes tibial plafond fractures and large posterior malleolar fractures)

0 to 2 weeks Gentle walking and elevation PWB

- Physiotherapy review post operatively for crutches
- Apply air-cast boot in theatre after surgery – No inflation
- **PWB (partial weight bear)** in air-cast boot with crutches is ok
You may opt to NWB (non-weight bear) due to pain, this is ok too.
After 3-5 days start to try and take some weight (<50% of your weight) on your

foot with the boot

- Keep boot on at all times - leave on 24/7 but check your skin underneath by undoing daily to view your skin by removing the front panel
- Rest and elevate to allow for wound healing – aim to keep your leg elevated 23hrs/day
 - When sitting elevate your leg on a foot stool, chair or up on sofa
 - When lying down, you can elevate your leg on a single pillow
 - Don't walk too much, aim for essential walking within your home in the first week
- Do not get dressings wet – cover your lower leg in a cast bag for showering
- Leave dressings intact for 10-14 days - until the '2 week' follow up
- Around 2 weeks you will have dressing removed and wound reviewed by a doctor
- A tubi-grip will be applied and the air-cast boot re-applied
- Teach application of air-cast boot – **but not to inflate for first 2weeks** and until dressing removed

Video demo: <https://www.youtube.com/watch?v=XnBm68oTDOw>

Crutches PWB = Partial Weight Bear

= <50% of your body weight

Boot on at all times

- Aim for ankle in neutral (90°)
- Can be refitted if needed to ensure heel down
- Or to check skin condition daily.

[figure not shown]
Walking with crutches:

- Crutches in front first, boot foot next taking **Partial weight** as pain allows (**up to 50% of your body weight**), good foot follows stepping up to (not past) operated foot (can use scales to check weight you're

2 to 6 weeks Progress more weight onto foot and start ankle movement WBAT

WBAT (weight bear as tolerated = up to full weight) in air-cast boot with crutches, boot inflated

- Boot on for all walking using 2 crutches
- You may be able to manage with 1 crutch indoors (crutch in opposite hand to foot)
- If painful or limping continue with 2 crutches
- Aim for step-through gait – Physiotherapist to review and advise

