APPENDIX 2: Rehabilitation timeline

Rehabilitation strategy

Patients will be followed up at 2, 6 and 12 weeks after their surgery (as per standard clinical care), at physiotherapy and orthopaedics department outpatient clinics at the Royal Brisbane and Women's Hospital (Brisbane, Queensland, Australia) (**Error! Reference source not found.**). Physiotherapy appointments will occur in fortnightly intervals from week 2 post-operatively. In total, patients will receive 6 sessions of physiotherapy treatment. Outcome measures will be recorded on the 1st, 3rd and 6th attendance of the patient for their physiotherapy and orthopaedic follow-up appointments (wks 2, 6 and 12 post-operatively).

[figure not shown]

Figure 2. The patient's postoperative timeline, including assessment time points.

The rehabilitation exercises that patients will be instructed to do are described in APPENDIX 2. The information booklet provided to patients will include instruction sheets with cartoons showing how to perform each of the exercises (Appendix 1). Patients will be advised as to their rehabilitation, pain relief and the Aircast boot according to the information in (Appendix 1). The wound dressings will be left intact until the first follow-up visit, 10 to 18 days after surgery.

Surgery date to 2 weeks post-surgery: Gentle walking and Elevation (**Error! Reference source not found.**)

[figure not shown]

Figure 3. The patient's postoperative timeline from surgery to assessment 1.

Aircast boot

The Aircast boot should remain on at all times and **should not be inflated during the first two weeks of the postoperative period**. During showering/bathing, the cast should be covered using a plastic bag, to ensure the boot and wound dressings do not get wet.

Charlson Comorbidity Index

Chart review version

Components of classical Charlson Comorbidity Index¹

1. Has the patient had a myocardial infarction? (MI)

- No
 Yes

Criteria: Myocardial infarction includes patients with one or more definite or probable myocardial infarction. These patients should have been hospitalized for chest pain or an equivalent clinical event and have had electrocardiographic and/ or enzyme changes. Patients with electrocardiographic changes alone who have no clinical history are not designated as having had an infarction.

2. Has the patient been hospitalized or treated for heart failure? (CHF)

- No
 Yes

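### In weeks 0–2 one daily charge of about 16 h cannot cover round-the-clock boot wear, so the charge question and the time-based loading measures need to be tied to recorded hours

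*Protocol*

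**What the plan says.** **Battery.** Section 3.1 says the device "can collect approximately 16 hours of data on a single charge". Section 2.10 repeats the figure: "the Magnes smart device has a battery life of appx 16 hours".

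**Charging.** Section 2.10: "Patients will be advised to charge the battery every day". Section 6.0: "they will be required to charge the Magnes device once a day". Neither section gives a time of day, a charging duration, or whether the device records while on charge. Section 2.10 also says that charging is the only thing the patient has to do with the device.

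**Wear, surgery to week 2.** Appendix 1: "Keep boot on at all times - leave on 24/7". Appendix 2: "The Aircast boot should remain on at all times". The leaflet also aims for 23 h of leg elevation a day in this period.

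**Wear afterwards.** Appendix 1 lets the boot come off at night from week 2, has it removed three times a day for exercises, and weans it from week 6.

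**What depends on the recording.** Aim 1 in section 3.1 covers the boot phase. It lists "Percentage of weight-bearing per week" and a correlation of instructed with actual weight-bearing in both intensity and total time. Section 3.2 uses the first download, at 2 weeks, to judge how the foot has been used and loaded since the operation. Table 1, row 2 (section 4.0) asks, at 2, 6 and 12 weeks, "Did the device remain charged (and able to record data) for the time period in question", together with daily wear time and any charging problems.

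**The concern.** In weeks 0–2 a patient who follows every instruction still has hours in the boot that the device cannot record. This matters in two places.

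First, maintaining charge is an acceptability outcome under Aim 1. If the row 2 question is read literally over a period of continuous wear, the answer is no for everyone because of battery capacity. It then says nothing about whether patients manage the charging.

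Secondly, the total-time comparison and the 2-week evaluation both depend on how long the foot was loaded. The protocol does not tie either of them to recorded hours. A shorter recorded loading time can mean less loading or less recording. Device feasibility is the primary objective and the target is 12 patients, so how much of the wear time was captured is itself something the future trial will need to know.

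**Working it through.** The protocol states no coverage figure, so there is nothing to reproduce. The check is arithmetic on its own inputs.

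**Inputs from the protocol**
- Recording per charge: about 16 h (sections 2.10 and 3.1).
- Charges per day: one (sections 2.10 and 6.0).
- Wear in weeks 0–2: 24 h a day for 14 days (Appendices 1 and 2).
- Elevation in weeks 0–2: 23 h a day (Appendix 1).

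**Assumptions**
- One full charge a day, continuous recording until the battery is flat, and no recording while charging.
- In weeks 2–6 (28 days), the boot is off for 6, 8 or 10 h at night. The protocol allows removal at night but gives no hours. The daytime removals for exercises are ignored.

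**Formula.** Unrecorded share of wear time = max(0, wear hours − 16) / wear hours, per day.

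**Weeks 0–2**
- (24 − 16)/24 = 8/24 = 33.3%.
- Wear: 14 × 24 = 336 h. Recordable: 14 × 16 = 224 h. Unrecorded: 112 h.
- If the approximate figure means 18 h: 6/24 = 25%. If it means 14 h: 10/24 = 42%.

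**Weeks 2–6, and weeks 0–6 together**

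| Boot off at night (assumed) | Wear per day | Unrecorded, weeks 2–6 | Unrecorded, weeks 0–6 |
|---|---|---|---|
| 6 h | 18 h | 2/18 = 11.1% | (112 + 56)/(336 + 504) = 168/840 = 20.0% |
| 8 h | 16 h | 0% | 112/(336 + 448) = 112/784 = 14.3% |
| 10 h | 14 h | 0% | 112/(336 + 392) = 112/728 = 15.4% |

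**What this does to loading time.** The loss of wear time is not the loss of loading time. If loading were spread evenly over 24 h, recorded loading time in weeks 0–2 would be 16/24 = 67% of the true value. With 23 h of elevation, however, only about 24 − 23 = 1 h a day is left for loading, against an 8 h gap. That hour can lie wholly outside the gap, in which case nothing is lost, or partly or wholly inside it. The timing of charging decides which, and the protocol does not fix it.

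**The case against.** Four counter-arguments deserve weight.

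1. **The conflict is brief.** This stands. A reader might infer that a third of all wear time is lost. The documents do not support that: the round-the-clock instruction ends at 2 weeks, night removal follows, and the shoe phase of Aim 2 has no such instruction.

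2. **The weekly percentage may not be a share of time.** This stands too. Section 3.1 gives no denominator. Appendix 1 sets partial weight-bearing as a share of body weight, and section 3.0 (under clinical outcomes) interprets force in newtons as weight-bearing. A mean or peak load over recorded steps would not fall merely because hours were missing. The point therefore rests on the total-time comparison and the evaluation since surgery, and reaches the weekly percentage only if that is time-based.

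3. **Nothing says that gaps count as no load.** Correct. A reader might infer that a flat battery is analysed as zero load, or that it passes for good adherence to the load limit. No section codes gaps as zero, and gap handling may be set out in an analysis plan that is not at hand. The early limit is an intensity, below 50% of body weight, and a missing reading does not imitate a low one. Row 2 also asks about wear time and charging problems, so gaps are partly identifiable. It relies on questions at only three visits, though, and the week 2, 6 and 12 forms in Appendix 5 show no field for wear, charge or recorded hours.

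4. **The device might record on charge, or recording might be paused.** The first is possible, and the protocol is silent on it. As to the second, section 3.1 mentions start/stop control through an app, but section 2.10 leaves the patient nothing to do except charge, and no section asks anyone to pause recording at rest.

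What survives is the mismatch in weeks 0–2. No later analysis can recover hours that were not recorded.

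**Conclusion.** The point holds for weeks 0–2. On the protocol's own figures, one daily charge covers at most about two thirds of instructed wear time. About 112 of 336 h per patient go unrecorded (25% to 42% of wear time for a battery of 18 to 14 h), provided that the device runs continuously and does not record on charge. In weeks 2–6 the loss is about 0–11% under the assumed nights out of the boot.

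Two consequences follow. The row 2 charge question, read literally, has an answer fixed by the battery in this period. The Aim 1 total-time comparison and the 2-week evaluation can understate loading by an amount that the documents do not determine. It is near zero if the gap falls in resting hours and larger if it does not. No single percentage bias in loading can be claimed.

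**What to change.** 1. **Charging outcome.** Take recorded hours per calendar day from the downloaded device file and judge them against the roughly 16 h that the battery allows. Keep the row 2 questions as supporting information, without relying on the charge question alone.
2. **Loading outcomes.** Express time-based outcomes per recorded hour or recorded day, and state that denominator in section 3.1. Treat unrecorded time as missing, and report coverage separately for weeks 0–2, weeks 2–6 and the shoe phase.
3. **Charging time.** Ask patients to charge at a standard time in resting hours. Before this is written in, the team should confirm how long charging takes, whether the device records meanwhile, and whether charging is compatible with the wear instruction. Sections 2.10, 3.1 and 6.0 and Appendices 1 and 2 then need to be reconciled. Which wear instruction should apply is a clinical matter, and none is proposed here.

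**Cost.** Wording in sections 2.10 and 3.1 and Table 1, row 2, plus a data field for recorded hours. The hours should come from files that are downloaded anyway. The small downside is that steps taken during the charging period, typically at night, are openly not captured.

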2.3 Interventions

The study will assess acceptance and interaction of patients and clinicians to implementation of a smart device to monitor weight-bearing during the rehabilitation phase following surgery of an unstable ankle fracture. Postoperative rehabilitation will be standardised for the initial 12-week rehabilitation period for all included patients, in accordance with current clinical practice. The patients' weight-bearing and activity will be recorded with the Magnes device.

This study does not examine the effectiveness of surgical or rehabilitation strategies. However, clinical outcomes will be recorded to allow exploration of the correlation between weight-bearing activities, clinical progress and adverse events. The future application of the Magnes device would allow to detect aberrant movement patterns early, hence avoiding complications following ankle fracture fixation.

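### A correlation between instructed and actual weight-bearing cannot show whether instructions were followed when the instruction is the same for nearly everyone in each phase

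*Protocol*

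**What the plan says.** Section 3.1 names the statistic. For the boot (Aim 1, week 1 to about week 6) it is "The correlation between instructed amount of weight-bearing and actual weight-bearing, in both intensity and total time". For the shoe (Aim 2, about week 6 to week 12) it is "The correlation between instructed amount of weight-bearing and actual weight-bearing". It is one of two feasibility outcomes in Aim 1 and one of three in Aim 2, and Section 3.0 makes feasibility outcomes the key outcomes.

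The instruction is meant to be common to all patients. Section 2.3 states: "Postoperative rehabilitation will be standardised for the initial 12-week rehabilitation period for all included patients, in accordance with current clinical practice". Section 2.7.2 excludes patients who "Require non-standard postoperative care". Appendix 1 gives one weight-bearing level per phase:

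- Weeks 0 to 2: partial, below 50% of body weight; bearing no weight because of pain is also acceptable.
- Weeks 2 to 6: as tolerated, up to full weight, in the boot.
- Weeks 6 to 8: full weight. No new level is given for weeks 8 to 12.

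Some text allows variation. Appendix 1 describes itself as a guide that the surgeon's plan may alter. Sections 2.8 and 3.2.1 make the move to the shoe typical at about 6 weeks and dependent on healing.

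The device "provides data in force measurements (Newtons) which will be interpreted as weight-bearing". Aim 2, but not Aim 1, also lists "Time to fully weight-bear".

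**The concern.** Comparing instructed with actual load has one evident purpose: to see whether patients did what they were told. Section 1 names the reliance on patient recall for adherence as a key challenge. A correlation needs an instruction that varies, and it ignores level. Here the instruction barely varies, and in the first two phases it is a ceiling or as tolerated, so there is no target to correlate with. A high coefficient could be carried into the planned randomised trial as evidence of compliance when limits had been exceeded, or when patients had loaded far less than they were allowed.

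The total-time part of the Aim 1 outcome has a further gap. The leaflet instructs no weight-bearing time. The nearest item is the aim in weeks 0 to 2 of keeping the leg elevated 23 hours a day.

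**Working it through.** The protocol gives no coefficient, threshold or variance, so there is no figure to reproduce. The loads and SDs below are assumptions for illustration. The instruction is coded from Appendix 1 as 50 for weeks 1-2 and 100 for weeks 3-6. That coding is itself an assumption, because Section 3.2 and Appendix 1 disagree on weeks 0-2 (see Fix).

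**Weeks 6 to 12.** With every patient instructed 100%, the variance of the instruction is 0. Pearson's r divides by its square root, so r is undefined. The same holds within weeks 0-2 alone or weeks 2-6 alone. Suppose instead that 1, 2 or 3 of the 12 patients are instructed 50% (assumed loads about 45 and 90, SD 8). Simulated r then averages 0.86, 0.91 or 0.93 if they comply. It averages about 0 (95% of simulations between -0.59 and 0.58) if load is unrelated to instruction. The coefficient exists but is carried by those few patients.

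**Weeks 0 to 6 pooled.** With a two-level instruction, r reduces to

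r = (M2 - M1) x sqrt(p(1 - p)) / SD_total,

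where M1 and M2 are mean loads in weeks 1-2 and 3-6, and p = 4/6, so sqrt(p(1 - p)) = 0.471. The instructed values 50 and 100 drop out. Only the rise between phases and the total spread matter, so adding a constant to all loads, or multiplying them all by one factor, leaves r unchanged.

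*Adherent cohort.* Assumed weekly means are 25, 35, 55, 70, 80, 90% of body weight, with between-patient SD 8 and within-patient SD 6.
- M1 = 30, M2 = 73.75, difference 43.75.
- Variance between phases: 43.75² x 2/9 = 425.3.
- Variance of weekly means within phases: (2 x 25 + 4 x 167.2)/6 = 119.8.
- Patient and residual variance: 64 + 36 = 100.
- SD_total = sqrt(645.1) = 25.4, so r = 43.75 x 0.471 / 25.4 = 0.81 (simulation mean 0.82).
- Share of week 1-2 values above 50, with SD sqrt(100) = 10: the average of P(Z > 2.5) = 0.006 and P(Z > 1.5) = 0.067, which is about 4%.

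*Same cohort, 50 points more every week.* Difference and spread are unchanged, so r is the same. The share above 50 is the average of P(Z > -2.5) = 0.994 and P(Z > -3.5) = 0.9998, over 99%. Capping recorded load at 100% of body weight still gives r = 0.82 by simulation.

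*Overload in weeks 1-2 only.*
- +30 points: M1 = 60, difference 13.75; SD_total = sqrt(42.0 + 119.8 + 100) = 16.2; r = 0.40 (simulation 0.41).
- +50 points: M1 = 80, difference -6.25; SD_total = sqrt(8.7 + 119.8 + 100) = 15.1; r about -0.20 (simulation -0.20).

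A second set of assumed loads (flat within phase, SDs 8 and 5) gives the same picture:

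| Load, weeks 1-2 / 3-6 (% body weight) | r | Week 1-2 values above 50% |
|---|---|---|
| 40 / 90 | 0.93 | 14% |
| 70 / 120 | 0.93 | 98% |
| 15 / 65 | 0.94 | 0% |
| 90 / 100 | 0.47 | 100% |
| 100 / 100 | 0.00 | 100% |

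The first three rows describe quite different behaviour and share one value of r. The last two show that r can fall, but a low r does not by itself say whether patients loaded too much or too little.

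**The case against.** Two stronger readings are tempting, and the documents do not support either.

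- A reader might infer that r is undefined in weeks 6-12 as a matter of fact. That holds only if every patient is instructed full weight throughout. Appendix 1 allows the surgeon's plan to differ, and Section 3.2.1 ties the shoe to healing, so r may exist, although on a few patients.
- A reader might infer that r is blind to all overloading in weeks 0-6. It is insensitive to uniform or proportional shifts, but it responds strongly to overload confined to weeks 1-2.

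The rest of the case against has some weight. The weekly percentage of weight-bearing is listed beside the correlation in both aims, and load is to be plotted over recovery, so a uniform overload should be visible there. That limits the harm but does not make the correlation informative. The protocol calls the item feasibility, not adherence, and attaches no decision to it; reading it as adherence is an inference from Section 1. Coefficient type and pooling can be left to an analysis plan, but the protocol itself fixes the outcome as a correlation. Recording force in Newtons is not an error, since body weight is collected. Listing time to full weight-bearing under the shoe matches the leaflet's full-weight phase, and nothing says boot data would be ignored; this is a clarification only.

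It also cannot be claimed that a replacement needs no new data. The Appendix 5 dictionary has no field for the instruction a patient was given, and Section 3.1 does not establish that per-step load is exported.

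**Conclusion.** The point holds in a bounded form. As written, the correlation cannot show whether instructions were followed. In weeks 6-12 it is undefined if the leaflet is followed, and otherwise depends on a few atypical patients. Over weeks 0-6 it mainly measures the rise in load with time since surgery. Illustrative values of about 0.8 to 0.9 arise equally from adherent, uniformly overloaded and uniformly underloaded cohorts, while early overload alone lowers r without showing direction. The total-time comparison has nothing to be compared with.

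The numerical sizes rest on assumed loads, SDs and the 50/100 coding. The invariance to level and the zero-variance result do not depend on the assumed loads or SDs. In a single-group study of 12 patients with several other feasibility and acceptability outcomes, this should be fixed but is not critical.

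**What to change.** Replace the correlation in Aims 1 and 2 with agreement measures per patient and phase. Express load as a percentage of body weight: 100 x N / (kg x 9.81), with weight taken from the Demographics form.

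- Where a numeric ceiling was instructed: the share of loaded time (or of steps, if the device exports them) above it, and the mean excess.
- Where a numeric target was instructed: the mean signed difference, actual minus instructed.
- In as-tolerated weeks: describe load only.

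Summarise within each patient first, then across patients. Drop total time as a comparison with instruction; it can still be described.

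Add one REDCap field for the weight-bearing instruction given at each visit. Reconcile Section 3.2, which has partial weight-bearing begin after the first follow-up visit, with Appendix 1, which allows it in weeks 0-2; until then the instructed amount has no settled value in those weeks. State that time to full weight-bearing is derived from the combined boot and shoe record, because the week 2-6 instruction in the boot already reads "WBAT (weight bear as tolerated = up to full weight".

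The cost is one data field, reworded outcomes, the reconciliation and analysis code. No extra visit or device is needed.
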